#### 1. OBJECTIVES

# 1.1. Primary Objectives:

- **1.1.1.** To characterize the safety and tolerability of CB-103 in combination with Venetoclax in adolescent (12 to 18 years) and adult (19 to 60 years) patients with relapsed/refractory T-cell acute lymphoblastic leukemia (T-ALL) and T-cell lymphoblastic lymphoma (T-LBL).
- **1.1.2**. To assess the efficacy of CB-103 in combination with venetoclax by the overall response rate (ORR), defined as complete remission (CR) plus CR with incomplete blood count recovery (CRi) [1] plus partial remission (PR) [2], in adolescent and adult patients with relapsed/refractory T-ALL/T-LBL.

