#### 3. STUDY POPULATION

#### 3.1. Inclusion Criteria:

**3.1.1.** Adolescent (12 to 18 years) and adult (19 to 60 years) patients who have relapsed or refractory T-cell lymphoblastic leukemia (T-ALL) or T-Cell lymphoblastic lymphoma (T-LBL) according to 2017 WHO classification [29] and NCCN v1 2021 [30]:

Patients must have  $\geq 5\%$  blasts in the bone marrow as assessed by morphology on standard bone marrow biopsy and aspirate or less than 5% blasts in the bone marrow in presence of extramedullary relapse, excluding isolated central nervous system (CNS) relapse. However, if an adequate bone marrow sample cannot be obtained, patients may be enrolled if there is unequivocal evidence of leukemia with  $\geq 5\%$  blasts in the peripheral blood.

- **3.1.2.** Patients are eligible independently of Notch pathway activation in the leukemic blasts: however, a fresh marrow/blood sample must be obtained before starting the study treatment to classify the patients as being either Notch positive or negative.
- **3.1.3.** Leukemic blasts must express of at least 2 of the following immune phenotyping: CD1a, CD2, CD3, CD4, CD5, CD7, CD8, CD34, TCR $\alpha$ B, TCR $\gamma$ S, cyCD3
- **3.1.4.** Patients have adequate performance status (ECOG ≤2) for patients ≥16 years old, Lansky score >50 for patients <16 years old.
- **3.1.5.** Patients must be 12 to 60 years of age inclusive when signing the informed consent. For patients < 18 years of age, parent or legally authorized representative (LAR) should be willing and able to give informed consent. Non-English speaking patients are eligible for whom consent process will follow institutional guidelines.
- **3.1.6.** Patients with CNS disease are eligible.
- **3.1.7.** Patients must have adequate organ function and laboratory results (obtained within 14 days of enrollment):
  - **3.1.7.1.** Direct bilirubin  $\leq 2$  x upper limit of normal (ULN).
  - **3.1.7.2.** Serum creatinine  $\leq$  1.5 x ULN; or if serum creatinine > 1.5 x ULN, then serum creatinine clearance (CrCl)  $\geq$  50 mL/min (estimated by Cockcroft-Gault formula).
  - **3.1.7.3.** Alanine aminotransferase (ALT) and/or aspartate aminotransferase (AST)  $\leq$ 3 x ULN;  $\leq$ 5 x ULN in case of suspected leukemic liver involvement

Page | 9 04/25/2024

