#### 9.1.2. Response Criteria T-ALL:

- **9.1.2.1. CR** (Complete Remission): Absolute neutrophil count >  $1.0 \times 10^9$ /L, platelets >  $100 \times 10^9$ /L, red cell transfusion independence, and bone marrow with < 5% blasts. No evidence of extramedullary disease.
- **9.1.2.2. CRi** (CR with incomplete blood count recovery): Bone marrow with < 5% blasts, with peripheral neutrophils of  $\le 1.0 \times 10^9$ /L or platelets  $\le 100 \times 10^9$ /L.
- **9.1.2.3. PR** (Partial Remission): All of the hematologic values for a CR but with a decrease of at least 50% in the percentage of blasts to 5% to 25% in the bone marrow aspirate. No evidence of extramedullary disease.
- **9.1.2.4.** Relapse: Subsequent appearance, after achievement of CR, of  $\geq$  5% blasts in the bone marrow with confirmation by flow cytometry or the development of extramedullary disease after achievement of CR.

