#### 12. STATISTICAL CONSIDERATIONS

This is a phase II open-label single arm and single institution clinical trial to evaluate the efficacy and safety of CB-103 in combination with venetoclax in adolescent and adult patients with T-ALL/T-LL in first or second bone marrow recurrence refractory to initial induction therapy or refractory to at least one reinduction attempt. Up to 30 patients may be enrolled, without regard to Notch status; we anticipate that approximately 50% of these patients will be Notch positive. The primary efficacy endpoint of the study is overall response rate (ORR, including CR,CRi and PR rate) after the first two induction cycles, and the primary toxicity endpoint is the rate of toxic events, defined as a grade ≥3 non-haemtological AEs that are possibly or probably related to the study drugs (see Adverse Events (SAE) definition in section 9.2.2.1.) occurring during the 28 days of induction cycle.

We simultaneously monitor efficacy and toxicity using the Bayesian optimal phase 2 (BOP2) design [32]. Specifically, let n denote the interim sample size, and N denote the maximum sample size. Let  $Y_{eff}$  and  $Y_{tox}$  denote the binary efficacy and toxicity endpoints, with  $Y_{eff} = 1$  and  $Y_{tox} = 1$  indicating that patients experience efficacy and toxicity, respectively. We assume that the joint distribution of  $(Y_{eff}, Y_{tox})$  follows a multinomial distribution with four elementary outcomes:  $(Y_{eff}, Y_{tox}) = (1, 1), (1, 0), (0, 1)$  and (0, 0). Let  $\mathbf{p} = (P_{11}, P_{10}, P_{01}, P_{00})$  denote the probabilities of observing the four outcomes, and let  $P_{eff} = Pr(Y_{eff} = 1), P_{tox} = Pr(Y_{tox} = 1)$  and  $P_{efftox} = Pr(Y_{eff} = 1, Y_{tox} = 1)$ . When efficacy and toxicity endpoints are monitored separately, the joint distribution reduced to marginal distribution of efficacy and marginal distribution of toxicity, respectively.

The treatment is deemed unacceptable if  $p_{eff} \le 0.15$  or  $p_{tox} > 0.20$ . Thus, we will stop enrolling patients and claim that the treatment is unacceptable if

$$Pr(p_{eff} > 0.15|data) < \lambda \left(\frac{n}{N}\right)^{\alpha}$$

or

$$Pr(p_{tox} \le 0.20|data) < \lambda \left(\frac{n}{N}\right)^{\alpha/3},$$

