25/30     0.83 (0.66, 0.93)       26/30     0.87 (0.7, 0.95)       27/30     0.9 (0.74, 0.97)       28/30     0.93 (0.78, 0.99)       29/30     0.97 (0.82, 1)	23/30	0.77 (0.59, 0.88)
26/30     0.87 (0.7, 0.95)       27/30     0.9 (0.74, 0.97)       28/30     0.93 (0.78, 0.99)       29/30     0.97 (0.82, 1)	24/30	0.8 (0.62, 0.91)
27/30     0.9 (0.74, 0.97)       28/30     0.93 (0.78, 0.99)       29/30     0.97 (0.82, 1)	25/30	0.83 (0.66, 0.93)
28/30 0.93 (0.78, 0.99) 29/30 0.97 (0.82, 1)	26/30	0.87 (0.7, 0.95)
29/30 0.97 (0.82, 1)	27/30	0.9 (0.74, 0.97)
	28/30	0.93 (0.78, 0.99)
30/30 1 (0.87, 1)	29/30	0.97 (0.82, 1)
	30/30	1 (0.87, 1)

In secondary analysis, ORR will be summarized separately by Notch status as proportions with corresponding 95% Agresti-Coull confidence intervals. The difference in ORR between Notch groups will be assessed by Fisher's exact test.

Other measures of response (CR, Cri, PR, relapse, radiographic tumor response, CNS remission, CNS relapse) and minimal residual disease (MRD) will be summarized as proportions with corresponding 95% Agresti-Coull confidence intervals.

Duration of Response (DoR), Overall Survival (OS), and event-free Survival (EFS) will be summarized using Kaplan-Meier methods.

In exploratory analyses, correlations between ORR and pharmacokinetic and pharmacodynamics markers will be summarized. Rates of patients transitioning to Hematopoietic stem cell transplant (HSCT) will be summarized. Endpoints may be further summarized separately by Notch status.

Additional statistical methods may be used.

The Investigator is responsible for completing an efficacy/safety summary reports and submitting it to the IND Office Medical Affairs and Safety Group, for review and approval.

This should be submitted after the first 10 evaluable patients complete 1 cycle of study treatment, and every 10 evaluable patients, thereafter. Efficacy summary will be submitted for every 10 evaluable patients after they complete 2 cycles of therapy.

Page | 52 04/25/2024

A copy of the safety summary report should be placed in the Investigator's Regulatory Binder under "sponsor correspondence".

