# **Appendix 2 Revised Criteria for Response Assessment**

Response and Site	PET-CT-Based Response	CT-Based Response
Complete Lymph nodes and extra- lymphatic sites  Non- measured lesion Organ enlargement New lesions Bone marrow	Score 1, 2, or 3 with or without a residual mass on 5PS† It is recognized that in Waldeyer's ring or extranodal sites with high physiologic uptake or with activation within spleen or marrow (eg, with chemotherapy or myeloid colony-stimulating factors), uptake may be greater than normal mediastinum and/or liver. In this circumstance, complete metabolic response may be inferred if uptake at sites of initial involvement is no greater than surrounding normal tissue even if the tissue has high physiologic uptake Not applicable None No evidence of FDG-avid disease in marrow	Complete radiologic response (all of the following):  Target nodes/nodal masses must regress to 1.5 cm in LDi No extralymphatic sites of disease  Absent Regress to normal None Normal by morphology; if indeterminate, IHC negative
Partial	Partial metabolic response	Partial remission (all of the following)
Lymph nodes and extra- lymphatic sites	Score 4 or 5† with reduced uptake compared with baseline and residual mass(es) of any size At interim, these findings suggest responding disease At end of treatment, these	> 50% decrease in SPD of up to 6 target measurable nodes and extranodal sites When a lesion is too small to measure on CT, assign 5 mm X 5 mm as the default value

Non- measured lesions Organ enlargement  New lesions Bone marrow	findings indicate residual disease  Not applicable  None  Residual uptake higher than uptake in normal marrow but reduced compared with baseline (diffuse uptake compatible with reactive changes from chemotherapy allowed). If there are persistent focal changes in the marrow in the context of a nodal response, consideration should be given to further evaluation with MRI or biopsy or an interval scan	When no longer visible, 0 X 0 mm  For a node > 5 mm X 5 mm, but smaller than normal, use actual measurement for calculation  Absent/normal, regressed, but no increase  Spleen must have regressed by > 50% in length beyond normal  None  Not applicable

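### For patients with extramedullary disease the primary ORR has two conflicting PR rules, and nothing says which one counts

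*Combined protocol and SAP*

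**What the plan says.** Section 1.1.2 sets the ORR for T-ALL and T-LBL together, "defined as complete remission (CR) plus CR with incomplete blood count recovery (CRi) [1] plus partial remission (PR) [2". Section 12 gives the primary efficacy endpoint as "overall response rate (ORR, including CR,CRi and PR rate) after the first two induction cycles".

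Section 9.1.2.3, under the T-ALL heading, defines PR as CR-level blood values with marrow blasts at least halved, and ends "blasts to 5% to 25% in the bone marrow aspirate. No evidence of extramedullary disease".

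Section 9.1.3 is headed as additional criteria for T-LBL, but its text covers patients with extramedullary disease in general and refers them to Appendix 2. There, PR on PET-CT is a score of 4 or 5 "with reduced uptake compared with baseline and residual mass(es) of any size". On CT it is a fall of more than 50% in the sum of the products of diameters (SPD).

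Section 3.1.1 admits patients with "less than 5% blasts in the bone marrow in presence of extramedullary relapse".

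Section 9.1.2.2 defines CRi by marrow blasts below 5% with low neutrophils or low platelets. Unlike CR and PR in the same list, it does not mention extramedullary disease.

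After the ORR analyses, Section 12 says that "Other measures of response (CR, Cri, PR, relapse, radiographic tumor response, CNS remission, CNS relapse" and MRD will be summarized as proportions.

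**The concern.** One PR rule requires that extramedullary disease be gone. The other describes extramedullary disease that has shrunk but is still there. No section says how an Appendix 2 result combines with the marrow criteria, or whether an Appendix 2 PR is a PR for the ORR.

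One count of responders feeds the Table 18 looks at 10, 20 and 30 patients, the final rule of more than 5 responses in 30, and the comparison by Notch status. Duration of response also starts from PR or better (9.1.5). The trial is open-label and Section 9.1.3 leaves the radiographic response to the investigator, so the choice between the rules should not be left until individual results are known.

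**Working it through.** **1. The definitions applied to typical patients at the end of cycle 2.** The patients are hypothetical. In A to C a measurable mass has shrunk by 60% in SPD and remains visible.

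| Patient | CR | CRi (9.1.2.2) | PR (9.1.2.3) | PR (Appendix 2, CT) |
|---|---|---|---|---|
| A: T-ALL, marrow blasts at least halved and now 5–25%, counts recovered | No | No (blasts) | No (mass) | Yes |
| B: entered under 3.1.1 with <5% blasts and a mass; blasts still <5%, counts recovered | No (mass) | No (counts recovered) | No (mass; blasts not 5–25%) | Yes |
| C: as B, but platelets 90 × 10⁹/L | No | Yes | No | Yes |

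A gets opposite PR results under two rules that both apply to him by their text. B cannot reach a 9.1.2.3 PR by improving, because blasts already below 5% cannot fall to 5–25%. C has worse blood counts than B and the same mass, yet C is a responder by the letter of 9.1.2.2 while B can be scored a failure.

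The two PR rules are not incompatible in every case. Appendix 2 has a PET marrow row under PR, so a patient whose masses cleared but whose marrow did not could arguably meet both. The conflict is exact where a mass remains.

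**2. Reproducing the design.** Inputs from Section 12: λ = 0.57, α = 0.86, N = 30, looks at 10, 20 and 30, prior Dir(0.05, 0.1, 0.15, 0.7). The marginal priors are Beta(0.15, 0.85) for efficacy (0.05 + 0.1 = 0.15) and Beta(0.20, 0.80) for toxicity (0.05 + 0.15 = 0.20).

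- Efficacy cutoffs λ(n/N)^α: 0.2216, 0.4022, 0.57. Stop at ≤0, ≤2, ≤5 responses.
- Toxicity cutoffs λ(n/N)^(α/3): 0.416, 0.5075, 0.57. Stop at ≥3, ≥5, ≥6 toxicities.

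These are the Table 18 boundaries. Exact enumeration of the four-outcome multinomial over three groups of 10 gives these chances of claiming the treatment acceptable:

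| Table 19 scenario | Stated | Exact |
|---|---|---|
| 3 (ORR 0.30, toxicity 0.10) | 77.76% | 78.46% |
| 6 (ORR 0.15, toxicity 0.20) | 8.34% | 8.17% |
| 7 (ORR 0.20, toxicity 0.10) | 45.19% | 45.28% |

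All ten scenarios agree within 1 percentage point. The design arithmetic is sound; the open question is who counts as a responder.

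**3. If some true responses are not counted.** The documents give neither the share f of patients with extramedullary disease nor the share s of their responses that are PR with a residual mass. Assume f = 20–40% and s = 25–50%, with response equally likely with and without extramedullary disease. The lost share is L = f × s, from 0.20 × 0.25 = 5% to 0.40 × 0.50 = 20%. Counted ORR = 0.30 × (1 − L); toxicity stays at 0.10; the joint probability is scaled to 0.05 × (1 − L).

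| L | Counted ORR | Early stop | Claim acceptable |
|---|---|---|---|
| 0 | 0.300 | 14.0% | 78.5% |
| 5% | 0.285 | 15.4% | 75.6% |
| 10% | 0.270 | 17.1% | 72.1% |
| 20% | 0.240 | 21.8% | 62.9% |

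Against the exact baseline the loss is 78.5 − 75.6 = 2.9 to 78.5 − 62.9 = 15.6 points. If half of the 20% were captured as CRi, as patient C is, L would be 10% and the result 72.1%.

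**4. The opposite direction.** If CRi without an extramedullary clause lifted the counted ORR of an ineffective treatment from 0.15 to 0.20 (an assumption; toxicity 0.20, joint 0.05), the chance of claiming it acceptable would rise from 8.2% to 19.0%.

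**The case against.** Two stronger readings are tempting, and the documents support neither.

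A reader might infer from the Section 12 list that radiographic responses are excluded from the ORR. But CR, CRi and PR stand in the same list, and they make up the ORR. Being listed there cannot put an item outside it; the sentence is a component-by-component summary.

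A reader might also infer that the ORR is biased downward overall. CRi as written already counts some patients with a residual mass, and could count some who have not responded at all, so the net direction is not established.

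Other points in the plan's favor have weight. The headings permit a reading in which 9.1.2 serves T-ALL and 9.1.3 serves T-LBL, so that Appendix 2 PRs count for T-LBL; Appendix 2 itself calls its CT category a partial remission. Section 9.1.1 rests the ORR on an external guideline that is not reproduced, and a combining rule might be found there. Requiring that extramedullary disease be gone is a legitimate, stricter endpoint, not a counting error in itself. The Table 18 criteria are non-binding.

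What remains is this. The protocol never states the split by heading, and the text of 9.1.3 is not limited to T-LBL, so T-ALL with a mass stays unresolved on any reading. Whatever the external guideline holds, the protocol's own two definitions still conflict. Non-binding boundaries do not remove the need for a single definition of the reported ORR.

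**Conclusion.** The point holds as a contradiction in the primary endpoint for patients with extramedullary disease. It goes beyond missing detail, because two written rules give opposite results for the same eligible patient, and the final decision can turn on one such patient (5 or 6 responses in 30). This part rests on the text alone.

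The size is conditional. With 5–20% of true responses uncounted, the chance of claiming an effective and safe treatment acceptable is about 76% to 63%, against the stated 77.76%. Those shares are assumed, every such response is taken as lost, and CRi capture would make the loss smaller. No overall direction of bias is claimed.

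**What to change.** Before further response data are reviewed, put one composite rule for patients with extramedullary disease at baseline into 9.1.2, 9.1.3 and Section 12:

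- State that an Appendix 2 PR counts as PR in the ORR when marrow blasts are below 5% or meet the marrow fall in 9.1.2.3.
- Say explicitly whether the blood-count requirement of 9.1.2.3 applies to these patients.
- Reconcile CRi (9.1.2.2) in the same rule, so that residual extramedullary disease is treated alike whatever the counts.
- Use this definition for the ORR, Table 18 and duration of response.
- Report marrow and radiographic partial responses separately.

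The cost is wording, plus reclassifying any patients already assessed; marrow and PET-CT assessments are already scheduled. The downside is that the ORR pools two kinds of PR, which the separate reporting makes visible. The sponsor should also confirm that the 0.15 and 0.30 response rates suit the definition adopted.

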# 4.3.4. Survival Follow-up

Page | 14 04/25/2024

Patients will be followed-up for survival data up to 2 years after their study enrollment: survival status and any new anti-cancer therapy may be collected by phone every 3 months.

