- 14. Lumbar puncture (T-ALL/T-LBL) for prophylactic intrathecal therapy: if prophylactic intrathecal therapy is foreseen by the treating physician, a lumbar puncture may be performed up to 3 days before the first dose of CB-103, and may be repeated at the discretion of the treating physician at the end of the first cycle and at the end of any subsequent cycles on or around day 28. If clinically feasible, one additional sample will be collected to determine the exposure of CB-103 in the CSF (this measurement will be done by a designated laboratory under Cellestia's responsibility).
- 15. For patients with PR or stable disease (SD) after the induction cycle(s) who may receive add-on selective therapy chosen by the investigator on the basis of the ongoing biomarker expression of the disease while continuing the treatment with the combination of CB-103 and venetoclax, the add-on therapy will be reported in details on the CRF.
- 16. EoT visit is to be done 5 days after the last dose of any study treatment, unless the patient starts any subsequent antitumor therapy (in which case the EoT visit should be performed before the start of the new therapy, whenever possible).
- 17 First follow-up visit will be 26 days after EoT (± 5 days), and every three months (± 14 days) thereafter, until EoS (i.e., death, patient's refusal, lost to follow-up) or study termination, whichever occurs first. Survival status and information on posterior antitumor therapies will be collected, telephone contact being acceptable.
- 18. If patient discontinued treatment without progression, tumor assessment will be done until progression or start of new antitumor treatment.
- 19. In case of relevant related toxicities (i.e., Grade>1), every 4 weeks until resolution or stabilization: information collected by telephone contact is acceptable.
- 20. Hepatitis B, C infection, and HIV will be obtained within 21 days of start of treatment.

Protocol 2021-0547 4/25/2024

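### Relapse and CNS relapse are summarized as simple proportions with no time horizon or at-risk denominator, although observation for relapse ends at different times for different patients

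*Combined protocol and SAP*

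**What the plan says.** Section 12 groups relapse and CNS relapse with CR, CRi, PR, radiographic response and CNS remission as other measures of response: "relapse, radiographic tumor response, CNS remission, CNS relapse) and minimal residual disease (MRD) will be summarized as proportions", with 95% Agresti-Coull limits. It names no time point, no denominator and no handling of censoring or death. Time-to-event methods go to three other endpoints: "Duration of Response (DoR), Overall Survival (OS), and event-free Survival (EFS) will be summarized using Kaplan-Meier methods".

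Section 9.1.2.4 defines relapse as "Subsequent appearance, after achievement of CR, of" marrow blasts at or above 5%, confirmed by flow cytometry, "or the development of extramedullary disease after achievement of CR". Only patients who have reached CR can therefore relapse. Section 9.1.4.2 defines CNS relapse as a new development, again without a window.

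Observation is arranged as follows:
- Section 4.2.3: CR/CRi patients may be treated until progression or transplant; PR and stable-disease patients receive at most three further cycles.
- Table 16, footnote 18: for patients who stop without progression, "tumor assessment will be done until progression or start of new antitumor treatment".
- Section 4.3.4: during the 2 years from enrollment, "survival status and any new anti-cancer therapy may be collected by phone every 3 months". Section 11 and Table 16 footnote 17 describe the same content.
- Table 16, footnote 14: repeat lumbar punctures are at the treating physician's discretion.

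**The concern.** Response after two cycles is a yes/no outcome on a common clock, and a proportion suits it. Relapse accrues over time and is seen only while someone is looking. A remitter who goes to other therapy after two months and one who is still in remission at two years contribute identically to a crude proportion. The result then depends on how long patients happened to be observed, and the error is in the favorable direction. The binomial limits treat every patient as fully observed.

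At stake is how the durability of remission is read, in a trial where moving to transplant is itself an exploratory objective (section 1.3.2).

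**Working it through.** **1. The plan's own interval figures.** Agresti-Coull uses ñ = n + z², p̃ = (x + z²/2)/ñ and limits p̃ ± z√(p̃(1−p̃)/ñ). For 7/30: ñ = 33.84, p̃ = 8.92/33.84 = 0.264, half-width 0.148, limits 0.12 to 0.41, as printed in Table 20. All 31 rows reproduce to two decimals. The interval arithmetic is correct; the question is what it is applied to.

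**2. Effect of unequal follow-up (assumed inputs).** The documents give no relapse or death rates and no accrual period. Assume exponential times with median 6 months to relapse and 12 months to a competing event, and follow-up C uniform over 1 to 24 months.
- λr = ln2/6 = 0.1155; λc = ln2/12 = 0.0578; Λ = 0.1733.
- 24-month cumulative incidence = (λr/Λ)(1 − e^(−24Λ)) = 0.6667 × (1 − 0.0156) = 0.656.
- Mean of e^(−ΛC) = (e^(−Λ) − e^(−24Λ))/(23Λ) = (0.8409 − 0.0156)/3.986 = 0.207.
- Expected crude proportion = 0.6667 × (1 − 0.207) = 0.529.
- Gap: 12.8 points.

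The same formulas at other medians:

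| Relapse / competing median (months) | Crude | 24-month incidence | Gap (points) |
|---|---|---|---|
| 12 / 6 | 0.264 | 0.328 | 6.4 |
| 4 / 6 | 0.532 | 0.599 | 6.7 |
| 6 / 12 | 0.529 | 0.656 | 12.8 |
| 12 / 24 | 0.402 | 0.583 | 18.2 |

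Crossing relapse medians 4, 6 and 12 with competing medians 6, 12 and 24 gives gaps of 6 to 18 points. Between those grid points it can be marginally larger (8 / 24: 0.516 against 0.703, 18.7 points).

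**3. Effect of leaving for transplant or other therapy (a separate model, also assumed).** Take median time to relapse 12 months (λr = 0.0578), death hazard 0.02 per month, a 24-month horizon, and departure independent of relapse. The true 24-month incidence is 0.628. The departure hazard is −ln(1 − p)/6 for a fraction p gone by month 6.

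| Gone by month 6 | Expected crude | Agresti-Coull coverage of 0.628, n = 30 / n = 9 | Mean Aalen-Johansen estimate, n = 30 / n = 9 |
|---|---|---|---|
| 25% | 0.437 | 44% / 83% | 0.625 / 0.609 |
| 50% | 0.296 | 3.5% / 53% | 0.593 / 0.533 |
| 75% | 0.187 | 0.1% / 23% | 0.492 / 0.398 |

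Here n is the number at risk; 9 is 30% of 30. Cumulative incidence is closer throughout, but it also falls short when few patients remain at risk.

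**4. When there is no bias.** With nobody leaving and 24 months of observation for all, the two figures agree (0.628 and 0.628). With nobody leaving but only 12 months of observation, the crude figure is 0.451.

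**5. Denominator.** Section 12 states only the enrollment ceiling ("Up to 30 patients may be enrolled, without regard to Notch status"). Three relapses would read 3/30 = 0.10 (0.03 to 0.26) or, with an assumed 12 CRs, 3/12 = 0.25 (0.08 to 0.54). The text does not say which group applies.

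**The case against.** The strongest reply is that relapse is already handled where it matters. Section 9.1.5 builds relapse into DoR and EFS, gives both a censoring rule at confounding anticancer therapy, and section 12 analyzes both by Kaplan-Meier. Relapse proportions are not among the secondary objectives in section 1.2, and section 12 allows additional methods. This stands as a limit on the harm. It does not remove the point: both endpoints are composites that include death, neither isolates relapse or CNS relapse, and permission to use other methods commits to nothing.

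A second reply is that a crude proportion is valid if the target is relapse before other therapy, with complete follow-up. That is true, but the plan states no such target.

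Four stronger readings are tempting and are not supported:
- *Relapse after transplant is never recorded.* Table 16 keeps disease assessment in the follow-up column, and footnote 18 does not name transplant. The documents show only that collection after new therapy or transplant is not planned.
- *Deaths cause the bias.* Cumulative incidence with death as a competing event also counts a death as no relapse. The bias comes from observation that ends early.
- *Relapse will be reported out of 30.* Table 20 illustrates response and toxicity rates. Section 12 carries over the interval method to relapse, not the denominator.
- *The 6 to 18 points measure loss to transplant.* They come entirely from the assumed uniform follow-up; the competing event is treated alike in both figures.

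**Conclusion.** The concern holds in this form. A simple proportion with Agresti-Coull limits is the wrong summary for relapse and CNS relapse here, because observation time differs by patient and neither horizon nor at-risk group is stated. Used as written, it understates relapse risk at a fixed horizon, and its limits are not valid for that risk.

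The direction is firm whenever some patients still at risk of relapse stop being observed before the horizon. The size is not: 6 to 18 points rests on exponential times and follow-up uniform over 1 to 24 months, and the larger shortfalls in the departure model rest on assumed departure rates. None of these figures predicts this trial's bias. With few remitters the sampling error will also be wide; 6/9, for example, has Agresti-Coull limits of about 35% to 88%.

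The matter is secondary and descriptive. The response/toxicity stopping rules and the final decision do not use it. It should be corrected because the error favors the treatment and the remedy is cheap.

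**What to change.** 1. Remove relapse and CNS relapse from the proportions sentence in section 12.
2. Report cumulative incidence of relapse from the date of CR among patients in CR, with death without relapse as a competing event. State whether CRi is included; if so, align section 9.1.2.4, which now defines relapse after CR only.
3. Censor at the last tumor assessment when new therapy or transplant starts, in line with section 9.1.5, and say explicitly that transplant is covered. Note that this assumes departure is unrelated to relapse risk, and show numbers at risk.
4. Report CNS relapse in the same way from C1D1 among patients who can newly develop it (not CNS-3 at baseline), or from CNS remission for those who reach it. CNS disease is eligible under section 3.1.6, so all treated patients is not the right set. State that lumbar punctures are discretionary; the method does not repair irregular CNS observation.
5. Optionally, record any reported relapse date at the existing 3-monthly contact, including after transplant. Label it reported, not protocol-confirmed, since a telephone report cannot meet the confirmation required in sections 9.1.2.4 and 9.1.4.2. Use it only in a sensitivity analysis.

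The cost is revised SAP wording, slightly more analysis work and, if step 5 is taken, one extra data item. The resulting relapse figure will probably be less favorable, with wide limits because few patients will be at risk.
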